2 STUDY DESCRIPTION

2.1 Study Design

This is a multicenter, randomized, double-blind, placebo-controlled study to assess the efficacy and safety of rimegepant in migraine prevention in Japanese subjects.

The study has 4 phases:

- Observation Phase (OP): Lasts approximately 28 days. Includes the Screening Visit and Prerandomization Evaluation Visit which must occur within 4 days of the Baseline Visit
- Double-blind Treatment (DBT) Phase:
 - Lasts up to 12 weeks, and includes the Baseline Visit, and Week 2, 4, 8, and 12/End of Treatment (EOT) Visits
 - Subjects are randomized 1:1 to one of the following 2 treatment groups at the Baseline Visit:
 - Rimegepant 75 mg dosed every other day (EOD)

- Placebo matching rimegepant 75 mg dosed EOD.
- Randomization is stratified by prophylactic migraine medication use (yes or no).
- Subjects are instructed that they can take a maximum of 1 orally disintegrating tablet (ODT) of double-blind (DB) study drug per every other calendar day.
- All randomized subjects who discontinue early from the DBT Phase should complete the EOT Visit. Otherwise, subjects should complete the Week 12 Visit.
- Open-label Extension (OLE) Phase:
 - Subjects who (1) complete the DBT Phase, (2) continue to meet all inclusion/exclusion criteria, and (3) have been compliant with the electronic diary (eDiary) may enter the OLE Phase, pending review of laboratory test results.
 - Lasts up to 40 weeks, and includes the Week 14, 16, 20, 24, 28, 32, 36, 40, 44, 48, 52/EOT Visits
 - Subjects are instructed that they can take a maximum of 1 open-label (OL) rimegepant 75 mg ODT (1) per every other calendar day on days they are scheduled to dose, and (2) as needed (pro re nata [PRN]) to treat a migraine on days they are not scheduled to dose.
 - All randomized subjects who discontinue early from the OLE Phase should complete the EOT Visit. Otherwise, subjects should complete the Week 52 Visit.
- Follow-up Phase:
 - Lasts up to 14 days and includes the Follow-up Week 2 Visit primarily for safety assessments. The Follow-up Week 2 Visit should occur approximately 2 weeks after the last visit in the last treatment phase (i.e., Week 12/EOT Visit if the subject did not enter the OLE Phase; Week 52/EOT Visit if the subject entered the OLE Phase).
 - All randomized subjects should complete the Follow-up Week 2 Visit, regardless of completing either treatment phase.

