- Total DB exposure (tablets) summed across all subjects, derived by summing cumulative DB exposure across all subjects
- Total DB exposure (patient-years), derived by summing (DBT end date DBT start date + 1)/365.25 across all subjects.

OL Rimegepant Exposure

OL rimegepant exposure is provided descriptively by treatment group/OL rimegepant and overall for the OL rimegepant safety analysis set, and includes the following parameters:

- Time on OL rimegepant (weeks), derived as (OL rimegepant end date OL rimegepant start date + 1)/7
- Time on OL rimegepant (weeks) categories: $\leq 12, \leq 24, > 24$
- Time on OL rimegepant milestone categories:
 - $\circ \geq 3$ months, defined as ≥ 11 weeks
 - $\circ \geq 6$ months, defined as ≥ 23 weeks
- Cumulative OL rimegepant exposure (tablets), derived by summing the number of tablets across records with complete dosing date and valid OL wallet number
- Average OL rimegepant exposure (tablets per month), derived as (1) cumulative OL rimegepant exposure if time on OL rimegepant < 14 days, or (2) 4 × cumulative OL rimegepant exposure/time on OL rimegepant if time on OL rimegepant ≥ 14 days
- Total OL rimegepant exposure (tablets) summed across all subjects, derived by summing cumulative OL exposure across all subjects
- Total OL rimegepant exposure (patient-years), derived by summing (OL rimegepant end date OL rimegepant start date + 1)/365.25 across all subjects.

DB or OL Rimegepant Exposure

DB or OL rimegepant exposure is provided descriptively by treatment group/OL rimegepant and overall for the DB or OL rimegepant safety analysis set, and includes the following parameters:

- Time on DB or OL rimegepant (weeks), derived as (DB or OL rimegepant end date DB or OL rimegepant start date + 1)/7
- Time on DB or OL rimegepant (weeks) categories: $\leq 12, \leq 24, > 24$
- Time on DB or OL rimegepant milestone categories:
 - $\circ \geq 3$ months, defined as ≥ 11 weeks
 - $\circ \geq 6$ months, defined as ≥ 23 weeks
 - $\circ \geq 1$ year, defined as ≥ 51 weeks.
- Cumulative DB or OL rimegepant exposure (tablets), derived by summing the number of tablets across records with complete dosing date and valid DB rimegepant or OL rimegepant wallet number

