 - Tablets per month are assessed by the number of 4-week (28-day) intervals in which a subject exceeded select tablet counts from the DB study drug start date to the DB study drug end date, where the number of 4-week intervals are consecutive (see Section 6.3.1.1 for months). For example, suppose a subject takes 20 tablets through 4 weeks, 10 tablets after 4 weeks to 8 weeks, and 25 tablets after 8 weeks to 12 weeks. Thus, this subject is not considered to have taken ≥ 14 tablets (more than EOD frequency) per month for 3 consecutive months.
- > 1 DB tablet taken on any 1 day
- ≥ 1 non-scheduled DB study drug dosing day (see Section 9.4)
- Incorrect DB study drug taken
 - All the time. Defined as as-treated treatment group not equal to as-randomized treatment group, i.e., any of the following:
 - Subjects randomized to rimegepant who took (1) ≥ 1 tablet from a DB placebo wallet, and (2) no tablets from a DB rimegepant wallet
 - Subjects randomized to placebo who took (1) ≥ 1 tablet from a DB rimegepant wallet, and (2) no tablets from a DB placebo wallet.
 - At least once. Defined as any of the following:
 - Subjects randomized to rimegpant who took ≥ 1 tablet from a DB placebo wallet
 - Subjects randomized to placebo who took ≥ 1 tablet from a DB rimegepant wallet.
- Time on study drug > 14 weeks.

Results for all categories are displayed, even those with 0 counts.

OL Rimegepant Treatment Compliance

The by-subject listing of OL rimegepant treatment compliance is provided for the safety analysis set, and displays results for OL rimegepant treatment compliance parameters in separate columns: average DB exposure (tablets per month; see Section 6.2.6.1); percentage for OL rimegepant tablet count compliance; flags for the other parameters ("Y" or missing).

The frequency table of OL rimegepant treatment compliance is provided by treatment group for the safety analysis set, and displays the following categories:

- OL rimegepant tablet count compliance ≥ 80% from OL rimegepant start to later of last scheduled OLE Phase visit or OL rimegepant end. Tablet count compliance is derived as 100 × cumulative OL rimegepant exposure/required cumulative OL rimegepant exposure, where
 - Cumulative OL rimegepant exposure is defined in Section 6.2.6.1.
 - Required cumulative OL rimegepant exposure is derived as follows:

- Let n = OL maxdate OL rimegepant start date + 1.

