 - OL maxdate is defined as the latest of the (1) Week 14, 16, 20, 24, 28, 32, 36, 40, 44, and 48 visit dates from the Visit Date OL CRFs, (2) Week 52/EOT visit date from the Visit Date OL CRF, if it is in the OL rimegepant safety analysis period (see Section 7.2), and (3) OL rimegepant end date.
- If n is even, then the required exposure is n/2.
- If n is odd, then the required exposure is n/2 + 1.
- Average OL rimegepant exposure (tablets per month) categories: ≤ 14, > 14 to ≤ 16, > 16, ≤ 17, > 17, > 18, > 19, > 20, > 22, > 24, > 26. Categories with 0 counts overall are not displayed. Average OL rimegepant exposure is defined in Section 6.2.6.1.
- > 1 OL rimegepant tablet taken on any 1 day
- Time on OL rimegepant > 44 weeks
- OL rimegepant start on or before DB study drug end. Defined as nonmissing OL rimegepant start date on or before DB study drug end date.
- OL rimegepant taken but DB study drug never taken. Defined as nonmissing OL rimegepant start date and missing DB study drug start date.

Results for all categories are displayed, even those with 0 counts except where noted.

eDiary Usage Compliance

eDiary Usage Compliance during the OP and DBT Phase

The table of eDiary usage compliance during the OP and DBT Phase is provided by treatment group for the DBT safety analysis set.

eDiary DBT usage compliance is derived as follows:

• DB study drug start to later of last scheduled DBT Phase visit or DB study drug end/OL rimegepant start: 100 × (total number of efficacy data days from the DB study drug start date to the DB maxdate)/(total number of days from the DB study drug start date to the DB maxdate), where DB maxdate is defined previously.

eDiary DBT usage compliance is summarized as a continuous variable, and as the number and percentage of subjects in the following categories: $\geq 90\%$ compliance; $\geq 80\%$ compliance.

In addition, the number and percentage of subjects with ≥ 24 days of eDiary efficacy data in the first 28 days of the OP are also provided; see Section 7.2 for the 28-day OP analysis period and Section 9.2.2 for eDiary efficacy data days.

eDiary Usage Compliance during the OLE Phase

The table of eDiary usage compliance during the OLE Phase is provided by treatment group/OL rimegepant and overall for the OL rimegepant safety analysis set.

eDiary OLE usage compliance is derived as follows:

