 - DB tablet count compliance < 80% from DB study drug start to later of last scheduled DBT Phase visit or DB study drug end/OL rimegepant start
 - Incorrect DB study drug taken
- OL rimegepant dosing issue, defined as any of the following subcategories (see Section 6.2.6.2)
 - OL rimegepant tablet count compliance < 80% from OL rimegepant start to later of last scheduled OLE Phase visit or OL rimegepant end
 - \circ > 1 OL rimegepant tablet taken on any 1 day
 - OL rimegepant start on or before DB study drug end

- OL rimegepant taken but DB study drug never taken.
- eDiary usage compliance < 80% from DB study drug start to later of last scheduled DBT Phase visit or DB study drug end (see Section 6.2.6.2)
- eDiary usage compliance < 80% from OL rimegepant start to later of last scheduled OLE Phase visit or OL rimegepant end (see Section 6.2.6.2)
- Prohibited non-study medications, defined as any of the following subcategories:
 - o Atypical antipsychotics taken on or after informed consent #
 - Botulinum toxin type A taken on or after informed consent
 - Butterbur root or extract taken up to 14 days before randomization or afterward
 - Calcitonin gene-related peptide (CGRP) antagonist monoclonal antibody or small molecule taken on or after informed consent #
 - o Ergotamine taken on or after informed consent
 - o Lamotrigine taken on or after informed consent
 - o Lasmiditan taken up to 14 days before randomization or afterward
 - Narcotic (barbiturate or opioid) taken up to 2 days before randomization or afterward #
 - Select moderate or strong cytochrome P450 3A4 (CYP3A4) inducer taken on or after informed consent #
 - Select strong CYP3A4 inhibitor taken on or after informed consent #
 - Traditional Chinese medicine taken up to 14 days before randomization or afterward#. These are identified by the sponsor medical lead or designee from reviewing a list of unique therapeutic class and preferred names.
 - Triptan as non-study OL rimegepant concomitant medication (see Section 6.2.6.3) #.

For the subcategories marked with "#", preferred names are displayed alphabetically as additional subcategories. Medications taken up to X days before a reference date or afterward are defined as those with imputed medication start date or imputed end date \geq reference date -X. Refer to the Core SAP for additional details about prohibited non-study medications, except for CYP3A4 inducers and inhibitors which are defined below.

Medication Group	Preferred Name

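### Open-label tablet-count compliance credits as-needed tablets against an every-other-day requirement, so the 80% category and the < 80% deviation flag can misclassify subjects who use as-needed tablets

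*SAP*

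**What the plan says.** SAP 2.1 describes an OLE in which subjects take a scheduled tablet every other day and may also dose "as needed (pro re nata [PRN]) to treat a migraine on days they are not scheduled to dose", with at most one tablet on a day. The phase "Lasts up to 40 weeks".

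SAP 6.2.6.2 gives open-label compliance as a ratio: "Tablet count compliance is derived as 100 × cumulative OL rimegepant exposure/required cumulative OL rimegepant exposure, where" the two terms are then defined. For the numerator it says "Cumulative OL rimegepant exposure is defined in Section 6.2.6.1", and that section reads: "Cumulative OL rimegepant exposure (tablets), derived by summing the number of tablets across records with complete dosing date and valid OL wallet number". Nothing there restricts the sum to scheduled dosing days. For the denominator, with n the number of days from open-label start to the last relevant date, "If n is even, then the required exposure is n/2"; odd n adds one. This is an every-other-day count with no PRN component.

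The ratio is used twice: for the category of at least 80% in the 6.2.6.2 frequency table, and in 9.1 as the dosing-issue deviation "OL rimegepant tablet count compliance < 80% from OL rimegepant start to later of last scheduled OLE Phase visit or OL rimegepant end".

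SAP 9.4 records that sites enter a dosing day type (scheduled or non-scheduled) for each dose date, with zero tablets marking a missed scheduled dose. It also classifies each open-label day as planned scheduled or planned non-scheduled.

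**The concern.** The numerator and denominator count different things. The numerator mixes scheduled and PRN tablets, while the denominator holds only scheduled ones. A PRN tablet on a non-scheduled day therefore cancels a missed scheduled dose, one for one.

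The same construction works in the double-blind phase, where no PRN use is planned and a separate category counts subjects with any non-scheduled dosing day. The open-label list has no such category. The other open-label dosing-issue deviations in 9.1 (more than one tablet in a day, open-label start on or before double-blind end, double-blind drug never taken) do not detect missed scheduled doses either.

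At stake is whether the 80% category and the < 80% flag say anything reliable about the preventive schedule in subjects who also dose as needed.

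**Working it through.** **Reproducing the SAP's own figures.** Every-other-day dosing over 28 days is 28/2 = 14 tablets. Then 80% = 11.2, 90% = 12.6, 110% = 15.4 and 120% = 16.8, which match the double-blind cut-offs printed in 6.2.6.2. The open-label denominator n/2 uses the same rate.

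**The SAP's own dosing example (9.4).** Scheduled doses fall on days 1, 3, 5, 8 and 10, and non-scheduled doses on days 6 and 14. Take the window as days 1 to 14, so n = 14 and the requirement is 14/2 = 7.

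- Planned scheduled days through day 14: 1, 3, 5, 7, 8, 10, 12, which is 7 days. Days 7 and 12 have no dose.
- As written: (5 + 2)/7 = 100%, not flagged.
- Scheduled tablets only: 5/7 = 71.4%, flagged.

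**A full 40-week OLE.** Assume n = 40 × 7 = 280. The requirement is 280/2 = 140 and the limit is 0.80 × 140 = 112. PRN tablets needed to pass = 112 − scheduled tablets taken.

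- 70% of scheduled doses: 98 taken, 112 − 98 = 14 PRN (1.4 per 28 days).
- 60%: 84 taken, 28 PRN (2.8 per 28 days).
- 50%: 70 taken, 42 PRN (4.2 per 28 days).

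PRN frequency is not in the documents, so it is treated as an assumption. Its ceiling is 28 − 14 = 14 per 28 days. The fewest scheduled doses that still reach 112 are:

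| PRN per 28 days (assumed) | PRN over 280 days | Fewest scheduled doses | Share of 140 | Missed |
|---|---|---|---|---|
| 0 | 0 | 112 | 80.0% | 28 |
| 1 | 10 | 102 | 72.9% | 38 |
| 2 | 20 | 92 | 65.7% | 48 |
| 4 | 40 | 72 | 51.4% | 68 |
| 8 | 80 | 32 | 22.9% | 108 |
| 11.2 | 112 | 0 | 0% | 140 |

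**No ceiling at 100%.** All 140 scheduled doses plus 4 PRN tablets per 28 days gives (140 + 40)/140 = 128.6%.

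**Is filtering the numerator enough?** Take scheduled doses on days 1, 3, 6, 8, 11, 13 and so on: 2 in every 5 days, or 112 in 280. Against n/2 this is 112/140 = 80%, not flagged. Under 9.4, days 5, 10, 15 and so on are also planned scheduled days, giving 3 in every 5, or 168. Adherence is then 112/168 = 67%. The denominator has to change too.

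**The case against.** The strongest reply is that scheduled adherence is reported elsewhere. The by-subject study drug listing in 6.2.6.1 shows dosing day type and keeps zero-tablet records on scheduled days. The table in 6.3.3.5 reports medication days on planned scheduled days, scaled to 14. Its rows for rimegepant alone and for rimegepant with acute migraine medication do not overlap, so their means add to the mean number of scheduled doses taken per 14 planned. This stands: missed doses are not lost. But neither output feeds the 80% category or the 9.1 flag.

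It is also fair that no result depends on the measure. No analysis set in 4.1 uses compliance, hierarchical testing (section 5 and 6.3.2.3) uses double-blind data, and OLE efficacy is descriptive. Significant deviations (6.2.4.2) come from a separate vendor file that may record poor dosing independently. This limits the consequence but does not repair the rule.

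A reader might infer that the study report will tell people scheduled dosing was followed when it was not. The documents do not support that. The category is labelled as a tablet count, and the table templates and Core SAP, which settle how it is presented, are not available here. A reader might also infer that the flag fails mainly in subjects with more migraines. That is plausible, but the documents give no PRN data to show it.

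**Conclusion.** The rule is wrong as written, with limited reach. PRN tablets enter the numerator and not the requirement, so the 80% category and the < 80% deviation can misclassify subjects who use PRN tablets. With no PRN use the inflation does not arise. At 4 PRN tablets per 28 days, a subject could miss 68 of 140 scheduled doses and still pass.

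These figures assume a full 280-day window and a calendar every-other-day schedule. The PRN rates are illustrative, so the number of subjects affected cannot be stated. The case with no scheduled doses is a boundary, not an expectation.

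The effect stops at descriptive OLE compliance and relevant-deviation reporting. It would be a mistake to carry it over to the primary, hierarchical or safety analyses. The point applies to C4951021, the study this SAP names. The protocol supplied is for C4951022, a single-dose study whose section 4.3.3 has no extension phase, so whether the parent protocol defines open-label compliance differently cannot be checked.

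**What to change.** In 6.2.6.2, and through it 9.1, define open-label scheduled-dose compliance as:

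100 × (scheduled OL rimegepant dosing days with a valid OL wallet number, at most 1 tablet per day) / (planned scheduled OL rimegepant dosing days by the 9.4 rule),

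with both counts taken over the existing compliance window. Use this ratio for the 80% category and the < 80% deviation. Report the all-tablet total as exposure only. Every scheduled dosing day is by definition a planned scheduled day, so the ratio cannot exceed 100%.

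Section 9.4 classifies days only within the open-label efficacy period, which ends one day after the last dose. The compliance window can run later, to the last scheduled visit, so the text should say that the 9.4 rule is applied through that date.

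The costs are modest: a little more programming with no new data, reliance on the site-entered dosing day type, loss of the exact parallel with the double-blind formula, and a less favourable stated open-label compliance. Because 9.4 restarts the schedule after each dose, a scheduled dose taken one day late counts as one missed day and one taken day, as days 7 and 8 do in the SAP's example. A late scheduled dose entered as non-scheduled would count as missed. Both conventions should be stated in a footnote. The change is to an analysis definition only and alters no dosing instruction.

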6.2.6.3 Non-study Concomitant Medications

Refer to the Core SAP for the following: definitions of select non-study medication types (i.e., previous, current, DBT concomitant, OL rimegepant concomitant, or follow-up); counting rules in non-study medication frequency tables; and non-study medication start and end date imputation.

The by-subject listing of non-study medications is provided by therapeutic class and preferred name for the enrolled analysis set. Acute migraine and prophylactic migraine medications are identified, as well as medication type.

The following conventions apply to non-study medications:

- Non-study medications are identified from those reported on the Concomitant Medication CRF. The Concomitant Medication CRF links medical history and AE terms respectively to the Medical History and AE CRFs.
- Prophylactic migraine medications are defined as those with "yes" response to the "Is this a prophylactic migraine medication?" question.
- Acute migraine medications are defined as those with "yes" response to the "Is this a rescue drug to treat a migraine?" question.
- Migraine standard of care medications are defined as acute migraine or prophylactic migraine medications.

Non-study DBT Concomitant Medications

Frequency tables of the following non-study DBT concomitant medications are provided by treatment group for the DBT safety analysis set: all; migraine standard of care; prophylactic migraine. Medications are displayed in descending order of rimegepant frequency within therapeutic class and preferred name.

Non-study OL Rimegepant Concomitant Medications

Frequency tables of the following non-study OL rimegepant concomitant medications are provided by treatment group and overall for the OL rimegepant safety analysis set: all; migraine standard of care; prophylactic migraine. Medications are displayed in descending order of overall frequency within therapeutic class and preferred name.

6.3 Efficacy

Efficacy endpoints are assessed by as-randomized treatment group.

Randomization is stratified by prior prophylactic migraine medication use (i.e., randomization stratum; yes or no). Hence, treatment group comparisons of continuous efficacy endpoints are *adjusted* by the randomization stratum, whereas treatment group comparisons of binary efficacy endpoints are *stratified* by the randomization stratum. If there is sparse data within a stratum, then results may be presented unstratified. Randomization is stratified using IWRS, but the randomization stratum used in analyses is based on actual data (i.e., stable prophylactic migraine medication use through randomization; see Sections 4.3 and 6.2.5.4). The rationale for using the actual data in analyses is that sites may erroneously report the wrong stratum in IWRS. Note that the phrase "randomization stratum" refers to the randomization stratum based on actual data, not IWRS, throughout this section.

In treatment comparisons of binary efficacy endpoints, confidence intervals (CIs) are based on a normal approximation to the binomial distribution using asymptotic standard error (ASE). Otherwise, CIs for continuous efficacy endpoints are based on the normal distribution. All CIs are 2-sided.

See Sections 7.2 and 7.3 for the definition of efficacy analysis periods and study days.

The by-subject listing of primary and secondary efficacy endpoints is provided for the full analysis set, and includes the reason for exclusion from the DBT migraine analysis set (see Sections 6.3.1 and 6.3.2): randomized more than once; not treated with study drug; treated with study drug and < 14 days of eDiary efficacy data in the OP; treated with study drug and < 14 days of eDiary efficacy data in all 3 months of the DBT Phase. Results for continuous endpoints are based on observed data, whereas results for binary endpoints incorporate missing data imputation. Subjects with \geq 14 days of efficacy data (not necessarily consecutive) in the month defining the endpoint are flagged for endpoints based on a single month.

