3.1.3 Exploratory Objectives

- 1. To evaluate the efficacy of rimegepant to placebo on the mean reduction from baseline in the number of migraine days per month by pain intensity (total; moderate or severe) in each month and the entire course of the DBT Phase.
- To evaluate the efficacy of rimegepant to placebo on the proportion of the subjects that have ≥ 50% reduction, ≥ 75% reduction, and 100% reduction from baseline in the number of migraine days per month by pain intensity (total; moderate or severe) in each month and the entire course of the DBT Phase.
- 3. To evaluate the efficacy of rimegepant to placebo on the mean reduction from baseline in the number of migraine days per week by pain intensity (total; moderate or severe) in each week of the first 4 weeks of the DBT Phase.
- 4. To evaluate the mean reduction in the number of migraine days per month by pain intensity (total; moderate or severe) in each month and the entire course of the OLE Phase.
- 5. To evaluate the proportion of the subjects that have ≥ 50% reduction, ≥ 75% reduction, and 100% reduction from baseline in the number of migraine days per month by pain intensity (total; moderate or severe) in each month and the entire course of the OLE Phase.
- 6. To evaluate the efficacy of rimegepant to placebo on the mean number of acute migrainespecific medication (i.e., triptans and ergotamine) days per month and acute migraine medication days per month in each month and the entire course of the DBT Phase.
- 7. To evaluate the mean number of acute migraine-specific medication days per month and acute migraine medication days per month in each month and the entire course of the OLE Phase.
- 8. To evaluate the mean changes from baseline in MSQoL domain scores, MIDAS scores, and EQ-5D-5L VAS score over time during the DBT and OLE Phases.

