6.3.2 Secondary Efficacy Endpoints

6.3.2.1 Percentages of Subjects with Reduction in Number of Migraine Days per Month

In analyses by months, subjects must (1) achieve the reduction criterion from OP in the number of migraine days in the specified month, (2) be evaluable (i.e., have ≥ 14 days of efficacy data [not necessarily consecutive]) in the specified month, and (3) have ≥ 1 migraine day (absolute not prorated to 28 days) of appropriate migraine severity in the OP analysis period to be classified as responders in the specified month. Otherwise, subjects are classified as failures in the specified month.

In analyses of the overall DBT (or overall OLE), subjects must (1) achieve the reduction criterion from OP in the number of migraine days in the overall DBT (or overall OLE), and (2) have ≥ 1 migraine day (absolute not prorated to 28 days) of appropriate migraine severity in the OP analysis period to be classified as responders. Otherwise, subjects are classified as failures.

Percentages of Subjects with Reduction in Migraine Days per Month in the DBT Phase

Analyses are based on the DBT migraine analysis set with eDiary efficacy dates in the OP and on-DBT efficacy analysis periods (see Section 6.3.1.1).

Treatment Group Comparisons

For each pain intensity (total; moderate or severe) and select percentage reductions ($\geq 50\%$, $\geq 75\%$, and 100%), the percentages of subjects with reductions are compared between treatment groups using Mantel-Haenszel risk estimation with stratification by randomization stratum (yes, no). This may be accomplished using SAS proc stdrate with the following options: method=mh, stat=risk, and effect=diff. Percentages are calculated against the number of subjects in the DBT migraine analysis set.

The table displays the following statistics at each month of the DBT Phase and overall DBT by pain intensity:

- Response rate (i.e., "n/N" and percentage), ASE, and 95% CI for each treatment group
- Stratified percentage difference between treatment groups (rimegepant placebo), ASE, 95% CI, and p-value
- Response rate (i.e., "n/N" and percentage), ASE, and 95% CI by randomization stratum for each treatment group
- Percentage difference between treatment groups (rimegepant placebo), ASE, 95% CI, and p-value by randomization stratum.

Results for \geq 50% reduction of moderate or severe migraine severity in the last 4 weeks (i.e., Month 3) support secondary objective #1. All other results support exploratory objective #2.

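### Wald intervals are prescribed for the exploratory ≥ 75% and 100% responder rows of the SAP, where they fail if responders are few; score-type intervals would be a cheap improvement

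*SAP*

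**What the plan says.** SAP section 6.3 (Efficacy) gives the rule for treatment comparisons of binary efficacy endpoints: "confidence intervals (CIs) are based on a normal approximation to the binomial distribution using asymptotic standard error (ASE"). Section 6.3.2.1, under its treatment group comparisons, takes three thresholds (≥ 50%, ≥ 75% and 100% reduction in migraine days), for total and for moderate or severe pain, "and 100%), the percentages of subjects with reductions are compared between treatment groups using Mantel-Haenszel risk estimation with stratification by randomization stratum" (yes, no).

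On layout, "The table displays the following statistics at each month of the DBT Phase and overall DBT by pain intensity". The required entries are rate, ASE and 95% CI per arm; the stratified difference; rate, "ASE, and 95% CI by randomization stratum for each treatment group"; and "Percentage difference between treatment groups (rimegepant placebo), ASE, 95% CI, and p-value by randomization stratum". On the denominator, "Percentages are calculated against the number of subjects in the DBT migraine analysis set". Section 6.3.3.2 repeats the same table for headache days.

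Two provisions deal with thin data. Section 6.3 allows results to be shown unstratified when a stratum is sparse. Section 4.3 allows subgroup levels to be redefined or combined, and randomization stratum is one of the listed subgroups. Neither names another interval.

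Only the ≥ 50% reduction in moderate or severe migraine days in Month 3 is in the tested hierarchy (secondary objective #1). The other rows serve exploratory objective #2. Sections 5 and 6.3.3 say that p-values for exploratory endpoints are descriptive and unadjusted.

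**The concern.** A normal-approximation interval takes its width from the observed proportion. When that proportion is zero, the estimated standard error is zero and the printed interval runs from 0% to 0%. When it is very small, the interval extends below zero and its upper limit is too low. The table applies this method to its most demanding responder definition, complete response, and then splits that row by stratum.

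No hypothesis test is at stake. What is at stake is whether the printed 95% intervals for exploratory objective #2 deserve the label. Because these rows carry no formal test, the interval is the main statement of uncertainty. There is also a reporting gap: if both arms of a stratum have no responders, the difference has standard error zero and the required p-value is undefined.

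**Working it through.** **Inputs.** About 225 evaluable subjects per arm (SAP section 5). This figure fits the plan's own power statement: with a 1-day difference, SD 3.75 and two-sided alpha 0.05, 1/(3.75 × √(2/225)) = 2.83 and Φ(2.83 − 1.96) = 80.7%, against the stated 80% or so. True response rates of 0.5% to 5% are assumed. Stratum sizes of 45 and 22 per arm (20% and 10% of 225) are also assumed.

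**Formulas.** Wald: p ± 1.96 × √(p(1 − p)/n), with p = x/n. Its lower limit is negative when x < 3.84 × (1 − x/n). For n = 225 and n = 45 that means x = 1, 2 or 3. Wilson at x = 0: upper limit 3.84/(n + 3.84), which is 3.84/228.84 = 1.68% for n = 225 and 3.84/48.84 = 7.87% for n = 45.

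**Per-arm intervals.**

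| Responders/n | Wald | Wilson |
|---|---|---|
| 0/225 | 0% to 0% | 0% to 1.68% |
| 1/225 | −0.42% to 1.31% | 0.08% to 2.47% |
| 2/225 | −0.34% to 2.12% | 0.24% to 3.18% |
| 3/225 | −0.17% to 2.83% | 0.45% to 3.85% |
| 5/225 | 0.30% to 4.15% | 0.95% to 5.10% |
| 0/45 | 0% to 0% | 0% to 7.87% |
| 1/45 | −2.08% to 6.53% | 0.39% to 11.57% |
| 3/45 | −0.62% to 13.95% | 2.29% to 17.86% |

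At n = 225 the Wald interval is 27%, 17%, 12% and 7% shorter than Wilson at 1, 2, 3 and 5 responders.

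**Per-arm coverage** (binomial probabilities summed over all x whose interval contains the true rate; chance of no responders = (1 − p)^n).

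| n | True rate | Chance of 0 responders | Wald | Wilson |
|---|---|---|---|---|
| 225 | 0.5% | 32% | 67.5% | 97.3% |
| 225 | 1% | 10% | 89.4% | 97.3% |
| 225 | 2% | 1% | 93.5% | 95.1% |
| 225 | 3% | 0.1% | 89.9% | 95.1% |
| 225 | 5% | about 0 | 92.6% | 95.4% |
| 45 | 1% | 64% | 36% | 92.5% |
| 45 | 2% | 40% | 60% | 94% |
| 45 | 4% | 16% | 84% | 97% |

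At n = 22 per arm, Wald coverage is 20%, 36% and 67% at 1%, 2% and 5%.

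**Differences.** With 0 against 0, Wald gives 0 to 0; Newcombe gives ±1.68 points at n = 225 and ±7.87 points at n = 45. With 1 against 0 at n = 45, Wald gives −2.08 to 6.53 points and Newcombe −5.85 to 11.57. Wald coverage at true rates of 2% against 0.5% is 92.3% at n = 225 and 67.6% at n = 45; at 5% against 2% it is 94.5% and 88.7%. When the two true rates are equal and very low, coverage exceeds 95%, because an interval collapsed at zero still contains the true difference of zero. The chance that both arms of a 45-per-arm stratum are empty, at 2% in each, is 0.98^90 = 16%. The overall stratified interval collapses only if every arm in every stratum is at 0% or 100%.

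**Tested endpoint.** At assumed rates of 50% against 35% and n = 225, Wald coverage of the difference is 94.6%.

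**The case against.** The strongest reply is that low counts are not established. A reader might infer that complete response over the whole double-blind phase means twelve weeks without a migraine day and must therefore be very rare. The SAP does not support that. Section 6.3.1.1 prorates overall migraine days over the available diary days. The overall responder rule in 6.3.2.1 has no 14-day condition for each month. The analysis set needs 14 diary days in only one month of that phase. A subject with about two recorded weeks free of migraine who then stops can count as a complete responder overall. The moderate or severe rows ask for less still, since only days of that severity must disappear. This part of the objection stands, so the low rates are an assumption.

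It is also fair to say that the table prints n/N beside each rate, so a reader can see a zero count, and that no decision rests on these rows. Both points limit the importance of the matter. Neither makes a 0% to 0% interval a valid 95% interval.

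The thin-data provisions answer less than they seem to. Both are optional and neither has a threshold. Showing results unstratified or merging levels can remove a thin stratum, but it leaves the interval method unchanged and does nothing for a whole arm with few responders.

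Finally, section 6.1.2 refers to a Core SAP for descriptive statistics. That document was not available and might bear on the per-arm rows. The rule for treatment comparisons is set in this SAP.

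**Conclusion.** The point holds as a conditional one. The SAP prescribes Wald intervals in rows where counts may be very low and provides no alternative. If true rates are about 1% or less in a whole arm, or up to about 4% in a stratum of 45 per arm, the stated 95% is materially wrong. At 2% to 5% with 225 per arm the shortfall is small, with coverage of about 90% to 94%. The rates and stratum sizes are assumptions, since the documents give neither.

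Three wider readings are not supported. The rule does not reach every binary result: the open-label responder tables specify no intervals. It does not concern the error bars in the figures, which belong to the migraine-day line plots. And it does not threaten the trial's conclusions: the primary endpoint is continuous, and the tested ≥ 50% Month 3 endpoint is not materially affected at mid-range rates.

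The SAP supplied is for the prevention study C4951021, whereas the protocol supplied is for the acute-treatment study BHV3000-313 (C4951022). The point concerns the SAP's study only.

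**What to change.** Add to SAP section 6.3, with a cross-reference in 6.3.2.1 and 6.3.3.2, a rule for the exploratory ≥ 75% and 100% reduction rows and their by-stratum rows:

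- Wilson score intervals for response rates.
- Newcombe intervals for differences, and stratified Newcombe for the stratified difference.
- The p-value shown as not estimable when no arm has a responder.

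Leave the ≥ 50% Month 3 analysis for secondary objective #1 as it is.

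The cost is a sentence or two and a routine programming change; no point estimate, hypothesis or sample size moves. There are two downsides. The intervals will not be symmetric about the estimate, and a Newcombe interval can occasionally disagree with the descriptive Mantel-Haenszel p-value in the same row, which a table footnote can explain. If response rates prove moderate, the two methods nearly coincide and little is lost.
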